#### **7.2.2. Dosimetry and Calculation of Absorbed Radiation Doses (Part 1 only)**

This will be conducted in Part 1 Cycle 1 only, and the timepoints for CSF/blood sampling and imaging scans are outlined in [Table 4](#).

**Table 4: CSF and Blood Sampling and Scans in only Cycle 1 of Part 1**

Time point (after dosimetry dose)	CSF	Blood	Whole-body planar Gamma Camera Scan	SPECT a
Baseline	×	×		
30 ( $\pm 10$ ) min b	×	×		
1 h ( $\pm 10$ min)	×	×		
4 h ( $\pm 10$ min)	×	×	× (+ 1 h)	
24 ( $\pm 2$ ) h	×	×	× ( $\pm 2$ h)	× ( $\pm 2$ h)
48 ( $\pm 2$ ) h	×	×	× ( $\pm 2$ h)	
72 ( $\pm 4$ ) h	×	×		× ( $\pm 2$ h)
Day 5-7 c	×	×	×	×
Day 15 ( $\pm 12$ h) d	×	×	×	×

Abbreviations: CSF = cerebrospinal fluid.

a SPECT scan is optional.b Both CSF and blood sampling; however, if both are not possible, CSF should be prioritized.c Can be performed on Day 8; however, must be prior to the treatment dose.d To be performed 7 days ( $\pm 12$  h) after the treatment dose.

A dosimetry dose of 5 mCi was selected, with a possibility to increase to 10 mCi at the Sponsor's discretion in case of too low acquisition of radioactivity count.

## Organ Dosimetry

Organ dosimetry by whole-body planar gamma camera scan (and regions of interest) will be conducted at site at the timepoints mentioned in [Table 4](#) and calculation of the absorbed radiation doses will take place centrally. If a hybrid planar/SPECT imaging scanner is available, SPECT images may be acquired to improve the quantitative assessment of tumor target absorbed doses in particular.

Regions of interest in each planar dataset will be defined for the following source organs at each timepoint if signal is visibly above the immediate background: brain, spinal cord, liver, thyroid, salivary glands, lungs, kidneys, bladder, gallbladder, stomach, spleen, heart, gastrointestinal tract (large and small intestines), and any other organs demonstrating appreciable uptake. The mean absorbed radiation dose in CSF and whole blood will be estimated via imaging-based estimation (CSF) and serial sample-based estimation (CSF and blood) as described in the technical operations manual.

Whole-body planar gamma camera (and SPECT, if possible) scans will be performed using a dual-headed gamma camera (e.g., ADAC dual-headed VERTEX gamma camera, Milpitas, CA) for both planar gamma and SPECT scans) or comparable dual-detector system with medium-energy collimation. A photopeak energy window of 208 keV ( $\pm 10\%$ ) and 113 keV ( $\pm 10\%$ ) is used for lutetium-177. A known activity (e.g., 100  $\mu$ Ci) of Lu-DTPA-omburtamab is placed alongside the patient (a minimum of 10 cm from an extremity) and serves as a calibration standard. Whole body and regions of interest are manually drawn. Spinal CSF is manually drawn on the posterior whole-body images.

## Absorbed Radiation Doses in CSF and Blood

The radioactivity in CSF and blood after administration of the dosimetry dose (seven measurements) and treatment dose (one measurement) in Part 1 Cycle 1 will be measured at site using a scintillation well counter, following qualified procedures outlined in the technical operations manual. The patients will have approximately 0.5 mL of CSF and 2 mL of peripheral blood drawn at each timepoint mentioned in [Table 4](#).

Upon local analysis, the data will be transferred to a vendor located in US for central evaluation of the radiation doses delivered to the CSF and blood (derived from radioactivity versus time data).

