#### **1.2.3.1. Radiotoxicity of Omburtamab Labels Other Than Lutetium-177**

A non-GLP study was conducted to evaluate radiotoxicity of I-omburtamab in 2 male cynomolgus monkeys given multiple doses of 3.62 to 8.3 mCi I-omburtamab via intrathecal injection. One monkey was preimmunized with I-omburtamab by IV administration 210 and 127 days prior to study initiation to evaluate anti-drug antibody (ADA) generation.

I-omburtamab produced detectable spikes of I-omburtamab in the CSF and comparatively lower levels of radiation in the blood. Suppressed levels in the blood of the preimmunized animal were likely due to a monkey anti-mouse antibody response that did not affect levels measured in the CSF. In general, total radioactivity elimination from the CNS was nearly complete by 48 hours post dose. I-omburtamab was tolerable for nontraumatic cisternal puncture. The findings associated with dosing, including changes in laboratory values measured in the CSF and blood, were transient and reversible. Beyond the injection site, no significant gross pathology or histopathological findings were noted in either animal and no long-term toxicities were observed after extended follow-up (i.e., >1200 days after the last dose).

Single-dose studies with the monoclonal antibody have been conducted for biotinylated omburtamab, I-omburtamab, and I-omburtamab in xenografted mice, naïve rats, or monkeys. The test agents were administered via IV or intratumoral infusions for mice, intraparenchymal infusion or convection-enhanced delivery for rats, and convection-enhanced delivery for monkeys. There was no evidence of neurological toxicity with biotinylated omburtamab. The radiolabeled antibodies were well tolerated in mice, rats, and monkeys at radioactivity doses up to 500 µCi I-omburtamab or 1 mCi I-omburtamab, the highest levels of radioactivity evaluated.

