#### **4.4. *Data Monitoring Committee***

An external DMC will be established to assure patient safety and will function independently of all other individuals associated with the conduct of the trial, including site investigators participating in the trial. The DMC will consist of a minimum of 2 physicians whose expertise covers relevant specialties.

During the conduct of Part 1, following completion of the first 5-week treatment cycle (Cycle 1) for the last patient in each dose level, the DMC will evaluate available safety information and recommend trial continuation or termination. If continuation is recommended, the DMC will recommend to the sponsor whether the dose should be escalated, de-escalated, or held at the same level. In the absence of DLT during the first two weeks of the first patient enrolled in each dose level, the enrollment to the dose level will continue without the need of feedback from the DMC.

If any of the side effects mentioned in the DLT definitions ([Section 3.1.1.2](#)) occurs during Cycle 2 in Part 1, these will be discussed at the first upcoming preplanned DMC meeting, and the internal Sponsor Safety Committee will evaluate the external DMC recommendations for further dosing. During Part 1 and until the DMC meeting in Part 2, the sponsor will share with the DMC all SAEs occurring during the trial and an unplanned DMC meeting can be held at the request of either the DMC or the Sponsor Safety Committee.

The DMC will evaluate the totality of cumulated absorbed dose calculated based on the dosimetry data from Part 1, and all available DLTs and other non-DLT toxicities from cycles 1 and 2 in all patients dosed in Part 1, to guide whether the maximum of five cycles is feasible in Part 2.

During the conduct of Part 2, an additional DMC meeting will be held when the eighth patient has completed dosing in Cycle 1 to evaluate whether the trial should be modified, stopped, or continue unchanged. The Sponsor Safety Committee will evaluate the recommendations from the DMC after each DMC meeting. Any significant finding/recommendation from the DMC and endorsed by the Sponsor Safety Committee will be communicated to the regulatory authorities and Institutional Review Board (IRB)/Ethics Committee (EC) as appropriate, and to the sites.

Responsibilities, procedures, content of the DMC packages, and workflow of the DMC are specified in the DMC Charter.

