## **8.6. Analysis for Calculation of Absorbed Doses to CSF and Blood (Part 1 only)**

The mean absorbed radiation dose in CSF and blood will be calculated from radioactivity measured in CSF and blood samples taken at predefined timepoints after the dosimetry and the treatment doses in Cycle 1.

Analysis of lutetium-177 activity in blood and CSF will include derivation of best-fit uptake and/or clearance parameters (elimination half-times, maximum value) of time-activity curves and of residence times (i.e., cumulated activity in  $\mu\text{Ci}\cdot\text{h}/\text{g}$ ). Blood and CSF time-activity curves will be modeled using exponential retention functions to estimate clearance following the last sampled timepoint, and cumulated activities for both will be computed using a combination of trapezoidal integration of sampling data and analytical integration of clearance curves (re-incorporating physical decay). Absorbed doses in the blood and CSF will then be derived from cumulated activity by applying the equilibrium absorbed dose constant for lutetium-177 under the assumption of complete local  $\beta$ -absorption, consistent with prevailing practice.

Individual and mean absorbed radiation dose to CSF and blood will be summarized using descriptive statistics for all patients in the Dosimetry Analysis Set and by trial site.

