 Given 1-2 hours prior to IMP administration, including oral acetaminophen/paracetamol and antihistamine (e.g., diphenhydramine).

 Following the dosimetry dose, whole-body planar gamma camera scans will be performed at 4 h (4-5 h), 24 h (22-26 h), 48 h (46-50 h), and Day 5-7 (may be performed on Day 8; however, must prior to the treatment dose), and on Day 15 (±12 hours), i.e., 7 days after administration of the treatment dose (see [Table 4](#)). SPECT imaging is optional at 24 h (22-24 h), 72 h (70-74), Day 5-7 (or Day 8 pre-dose), and on Day 15 (±1) (i.e., 7 days after the treatment dose).

 Approximately 0.5 mL of CSF and 2 mL of peripheral blood will be drawn at each timepoint (see [Table 4](#)), i.e., before treatment (baseline; to avoid withdrawing too high volumes of CSF on the day of the dosimetry dose, baseline sample should be drawn in the time between placement of the ICV access device and 1 day before dosing) and following the dosimetry dose at 30 min (±5 min), 1 h (±10 min), 4 h (±10 min), 24 h (±30 min), 48 h (±1 h) and 72 h (±4 hour). In addition, samples are drawn on Day 5-7 (may be on Day 8; however, must be prior to the treatment dose) and on Day 15 (±12 hr), i.e., 7 days after administration of the treatment dose.

 In accordance with [Appendix 1](#).

 If CSF cytology sample is positive, it must be repeated within 4 weeks of the positive sampling.

 Drawn and held for culture only if elevated body temperature after dosing suggests infection rather than expected response to ICV dosing. Samples to be taken within 6 hours after completion of IMP infusion.

 The baseline ADA samples must be drawn prior to the dosimetry dose and to avoid withdrawing too high volumes of CSF on the day of the dosimetry dose, the samples should be drawn in the time between placement of the ICV access device and 1 day before dosing. Serum and CSF samples for ADA analyses will be drawn at baseline and after last treatment. Presence of ADA will be analyzed at a central laboratory.

 Blood and CSF samples for pharmacokinetics will be drawn as per [Table 5](#). On Day 15 (i.e., 7 days after the treatment dose), blood collection only.

 Pregnancy testing (serum or urine) is mandatory for women of childbearing potential at screening, within one week prior to each dose, and at the EOT Visit.

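### Section 8.6 does not say which trapezoidal rule is used; in its ordinary linear form, with no CSF sample between 4 h and 24 h, it biases the sample-based CSF absorbed dose upward.

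*Combined protocol and SAP*

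**What the plan says.** **Schedule.** Table 4 (Section 7.2.2) draws CSF at baseline and at 30 min, 1, 4, 24, 48 and 72 h and Day 5-7 after the dosimetry dose. Footnote 13 of Table 6 repeats the later times as "4 h (±10 min), 24 h (±30 min), 48 h (±1 h) and 72 h (±4 hour"). The Day 15 sample follows the treatment dose and is not on this curve; Section 7.2.2 counts "dosimetry dose (seven measurements) and treatment dose (one measurement").

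**Integration.** Section 7.2.2 sends the site counts to a vendor for "central evaluation of the radiation doses delivered to the CSF and blood (derived from radioactivity versus time data"). Section 8.6 states that "cumulated activities for both will be computed using a combination of trapezoidal integration of sampling data and analytical integration of clearance curves". The blood and CSF curves are "modeled using exponential retention functions to estimate clearance following the last sampled timepoint". The section does not say linear or log-linear. Section 7.2.2 leaves procedures to a technical operations manual.

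**Second estimate.** Sections 7.2.2 and 8.7 also derive a CSF dose from planar scans. Those fall at 4, 24 and 48 h and Day 5-7, so they have the same gap.

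**Use.** CSF dosimetry is a Part 1 secondary endpoint (Section 2.2.2.1). On the number of Part 2 cycles, Section 4.4 says: "The DMC will evaluate the totality of cumulated absorbed dose calculated based on the dosimetry data from Part 1", together with DLTs and other toxicities from both cycles. Section 5.3.1 lets the calculated CSF and blood doses help guide individual dose reductions in Part 2.

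**Clearance.** For two monkeys given the iodine-131 product intrathecally, Section 1.2.3.1 reports that "total radioactivity elimination from the CNS was nearly complete by 48 hours post dose". Section 1.2.4 reports that in rats the lutetium product had left the vertebral canal and brain by 24 h. Neither gives a half-life.

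**The concern.** The product is infused into the CSF, so after mixing the CSF curve should decline. A chord across a convex decline lies above the curve. The 4-24 h interval is 20 hours long and, with rapid clearance, holds about half of the true area. As written, the exponential model does not bridge it.

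The resulting error has one sign in every patient with a declining curve, so averaging over patients does not remove it. It would enter the Part 1 summary of CSF absorbed dose and could enter the dose figures that the DMC sees.

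**Working it through.** The plan states no figure for CSF dose accuracy or CSF half-life, so there is none to reproduce.

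**Inputs**
- Sampling times from Table 4: 0.5, 1, 4, 24, 48, 72 h and Day 5-7, taken as 144 h. The curve is back-extrapolated to time 0.
- Effective half-life T (biological clearance and physical decay together): an assumption. If clearance by H hours means that a fraction r remains, T = H·ln 2 / ln(1/r). With 10% or 1% left at 24 h, T = 7.2 or 3.6 h; with the same fractions left at 48 h, T = 14.4 or 7.2 h.

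**Formulas**, for A(t) = exp(-ln 2·t/T), starting activity 1
- Exact area: T / ln 2.
- Linear segment of width h between values a and b: h(a + b)/2.
- Log-linear segment: h(a - b)/ln(a/b).
- Tail: last value divided by the slope from the last two points.

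**Worked case, T = 8 h**
- A(4) = 0.7071 and A(24) = 0.1250.
- Linear 4-24 h: 20 × 0.8321 / 2 = 8.32. Exact: 11.54 × (0.7071 - 0.1250) = 6.72. Excess: 1.60.
- All segments and tail: linear 13.68, exact 11.54, bias +18.6%. The 4-24 h interval supplies 1.60/11.54 = 13.9 points and the other intervals 4.7.

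**Single-phase decline, linear rule**

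| T (h) | Exact area | Linear area | Bias | Points from 4-24 h | Excess area (h) |
|---|---|---|---|---|---|
| 3.6 | 5.19 | 7.69 | +48.1% | 45.7 | 2.50 |
| 4 | 5.77 | 8.28 | +43.5% | 40.9 | 2.51 |
| 6 | 8.66 | 11.01 | +27.1% | 23.3 | 2.35 |
| 8 | 11.54 | 13.68 | +18.6% | 13.9 | 2.14 |
| 12 | 17.31 | 19.28 | +11.4% | 5.9 | 1.97 |
| 14.4 | 20.78 | 22.76 | +9.5% | 3.9 | 1.98 |
| 24 | 34.63 | 36.79 | +6.3% | 1.1 | 2.17 |
| 36 | 51.94 | 53.99 | +4.0% | 0.4 | 2.05 |

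The log-linear rule gives 0% in every row. Starting the curve at zero instead of back-extrapolating lowers the linear bias by about 1 to 5 points.

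Two features stand out. The excess area is nearly constant, at 2.0 to 2.5 hours of starting activity, so the large percentages belong to small totals. At T = 12 to 14.4 h, about half or more of the bias comes from intervals other than 4-24 h (5.5 of 11.4 points and 5.6 of 9.5).

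**Two-phase decline.** The grid had 36 curves: 70, 80, 90 or 95% clearing at 2, 2.5 or 3 h, and the remainder at 20, 30 or 40 h. Linear bias ran from +9.9% to +45.7%, log-linear from +5.1% to +17.5%. Log-linear was closer on all 36.

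**Blood.** On one-compartment uptake and clearance curves the linear rule erred by -1% to 0%, and a log rule on declining segments by -2% to -7%. Section 1.2.4 reports peak blood uptake at 24 h in rats, so the 4-24 h interval is probably rising. The linear rule suits blood.

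**The case against.** **The linear rule is not named.** This stands. A log-linear trapezoid is also a trapezoidal rule, and the technical operations manual may settle the matter. Section 8.6 also promises best-fit clearance parameters. A reader might infer that the plan commits to a biased calculation; the text supports only that the rule is unspecified and that its ordinary reading is linear.

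**The half-lives are assumed.** This also stands. The rat finding concerns canal and brain, the monkey finding concerns the CNS after the iodine-131 product, and Section 1.2.4 still found omburtamab in juvenile monkey CSF at 24 h. The human figure for the iodine-131 product, a mean of 0.60 Gy/mCi (range 0.17 to 2.07, Section 1.3), offers a rough bound. With 0.182 MeV per decay (Table 2) and an assumed CSF mass of 80 to 150 g, 1 mCi delivers 3.7×10⁷ × 3600 × 0.182 × 1.602×10⁻¹³ = 0.00388 J per hour, or 0.0485 to 0.0259 Gy/h. Then 0.60 Gy/mCi implies 12.4 to 23.2 h of starting activity, a half-life of about 9 to 16 h, and a linear bias of about +17% to +9%. A typical patient may therefore lie toward the low end. This rests on another isotope, instant mixing and an assumed mass.

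**The consequence is indirect.** A reader might infer that the DMC will receive a dose overstated by a known percentage. The documents do not say whether it receives the sample-based or the imaging-based estimate, they set no CSF dose threshold, and dosimetry is one input among several. Where CSF dose is highest, the error is smallest in relative terms.

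**Comparison with the iodine-131 product.** A reader might infer that a comparison with 0.60 Gy/mCi would be distorted. The documents do not give the integration method behind that figure, so this cannot be claimed.

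**Conclusion.** The point holds conditionally. The 4-24 h gap and the unqualified trapezoidal rule are in the documents, and so is the restriction of the exponential model to the period after the last sample. If the rule is applied linearly to a declining CSF curve, the sample-based cumulated activity and absorbed dose are biased upward: by about +10% to +50% if effective half-lives are about 3.6 to 14 h, and by about 6% or less at 24 h or longer. The first range rests on turning two qualitative animal statements into half-lives.

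The gap is the main cause only when clearance is fast. This is more than missing detail, because the ordinary reading of the stated rule biases a secondary endpoint and a better method exists for the same samples. It does not show that any DMC decision would change.

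**What to change.** In Section 8.6, and in the vendor's manual, state how CSF is integrated. The preferred wording is that the fitted multi-exponential curve is integrated over the whole time range. The alternative, or fallback where seven points do not support a multi-phase fit, is the log-linear trapezoid on declining CSF segments. Use actual sampling times in either case: Table 4 allows ±2 h at 24 h and footnote 13 of Table 6 allows ±30 min. Keep the linear rule for rising segments and for blood.

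The log-linear rule removes the bias for single-phase decline and leaves about +5% to +18% on the two-phase curves above, against about +10% to +46% for the linear rule. That residual is why the fitted curve is preferred, although between 4 h and 24 h its result rests on the model chosen. The same edit could state which CSF estimate goes to the DMC.

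The cost is a sentence or two in Section 8.6 and the manual. No extra sample, visit or patient is needed, and the 20 mL CSF limit in Section 7 is not affected.

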### 7.2.3. Magnetic Resonance Imaging

Brain and spine MRI for assessment of response should be done locally in accordance with the recommendations outlined by the RAPNO committee, including:

- Central review for eligibility by neuroradiologists (at site) with expertise in pediatric brain tumor imaging.
- Absence of movement artifacts- if judged necessary, the patient must be sedated.
- Available preoperative contrast-enhanced MRI, to allow sufficient delineation of primary tumor and assessment of leptomeningeal metastases.
- Slice thickness according to the recommendations in RAPNO (see Table 1 in [Warren et al. 2018](#)).
- Spinal MRI with full visualization of the dural sac, performed in 2 planes without skip regions and with adequate slice thickness and resolution.
- Tumor measurements should be made using the sequence that best demonstrates the extent of tumor; non-enhancing and enhancing primary lesions should be measured similarly.

### 7.2.4. CSF for Cytology, Total Protein, Glucose, ctDNA, and Cell Count

Samples of CSF for cytology, total protein, glucose, ctDNA, and cell count should be collected according to the Schedule of Assessments ([Appendix 3](#)). The CSF is sampled from the intracerebroventricular access device (e.g., Ommaya).

#### 7.2.4.1. *CSF Sampling for ctDNA Sequencing*

Samples of CSF for ctDNA will be collected in standard CSF collection kit via the Ommaya reservoir at screening and at the EOT Visit if the patient has given informed consent to DNA analysis. ctDNA will be sequenced using high-throughput DNA sequencing. Samples will be

stored at site until testing at a central facility. As per protocol version 8, this analysis will not be performed, and samples should no longer be shipped from sites.

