### **Evaluation: Dosimetry, imaging, and laboratory evaluations**

Patients will undergo:

- Clinical chemistry and hematology assessments.
- Blood and CSF draws for calculation of absorbed doses (Part 1 only).
- Whole-organ dosimetry measurements based on gamma (and SPECT, if possible) scans (Part 1 only).
- Brain and spine MRI.
- CSF sampling for cytology, total protein, glucose, circulating tumor DNA (ctDNA; if the patient has given informed consent to this analysis), and cell count.
- Blood and CSF draws for PK; and blood and CSF draws for anti-drug antibody (ADA) analysis and for potential culture (in case of elevated body temperature).

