## 7. TRIAL ASSESSMENTS AND PROCEDURES

Trial procedures and their timing are summarized in the Schedule of Assessments ([Appendix 3](#)). As protocol waivers or exemptions are not allowed, with the exception of immediate safety concerns, these should be discussed with the sponsor immediately upon occurrence or awareness to determine if the patient should continue or discontinue the IMP. Adherence to the trial design requirements, including those specified in the Schedule of Assessments, is essential and required for trial conduct.

All screening evaluations must be completed and reviewed to confirm that potential patients meet all eligibility criteria. The investigator will maintain a screening log to record details of all patients screened and to confirm eligibility or record reasons for screening failure ([Section 4.3.1](#)), as applicable. Procedures conducted as part of the patient's routine clinical management (e.g., blood count) and obtained before signing the ICF may be utilized for screening or baseline purposes provided the procedure met the protocol-specified criteria and was performed within the timeframe defined in the Schedule of Assessments ([Appendix 3](#)).

The maximum amount of blood collected from each dosed patient over the duration of the trial, including any extra assessments that may be required, will not exceed 300 mL, and the maximum amount of CSF collected from each dosed patient over the duration of the trial, including any extra assessments that may be required, will not exceed 20 mL. In case the patient will participate in the ctDNA analysis, additional 3-5 ml CSF will be collected. Repeat or unscheduled samples may be taken for safety reasons or for technical issues with the samples.

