## Appendix 3: Schedule of Assessments

**Table 6: Schedule of Assessments – Part 1, Screening and Cycle 1**

Dosing/Measurements/Evaluations	Screening	 Lu-DTPA-omburtamab Treatment Period  – Cycle 1				
	Day -29* to -1	Day 1	Day 8 (±1)	Day 15 (±1)	Day 22 (±1)	End-of-Cycle Visit (Day 29 [±1])
Informed consent 	X					
Eligibility check	X					
Demographics, height, body weight	X					
Medical, surgical, and disease history	X					
Prior/concomitant medications	X	X	X	X	X	X
Physical examination 	X					
Vital signs 	X	X	X	X	X	X
Performance test 	X 					
MRI of the brain and spine 	X 					
Neurological examination 	X	X				
Placement of indwelling ICV access device	X 					
ICV access device patency/CSF flow assessment	X					
Premedication (oral dexamethasone/IV equivalent) 		X	X			
Anti-pyretic and anti-histaminergic premedication 		X	X			
ICV  Lu-DTPA-omburtamab dosimetry dose		X				
ICV  Lu-DTPA-omburtamab treatment dose			X			
Whole-body planar gamma camera scan 		X 	X 	X 		
Blood and CSF for calculation of absorbed doses 		X 		X 		
Clinical chemistry and hematology 	X	X	X	X	X	X
CSF for cytology  , total protein, glucose, and cell count	X 					
Blood and CSF for culture		X 	X 			
Blood and CSF sampling for ADA 	X 					
Blood and CSF sampling for pharmacokinetics			X 	X 		
Pregnancy testing 	X	X	X			
Adverse events 	X	X		X	X	X

Abbreviations: ADA = anti-drug antibody; AE = adverse event; CSF = cerebrospinal fluid; ctDNA = circulating tumor deoxyribonucleic acid; EOT = end of treatment; HSA = human serum albumin; ICF = informed consent form; ICV = intracerebroventricular; IMP = investigational medicinal product; IV = intravenous; MRI = magnetic resonance imaging; NCI = National Cancer Institute; SAE = serious adverse event.

\* A longer screening period (e.g., due to logistics, COVID-19 situations etc.) are allowed; however, eligibility evaluation must be re-confirmed. Screening period of >60 days with individual patient considerations to be discussed with the sponsor.

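### Version 8 cancels the ctDNA analysis and sample shipment but leaves in force the instruction to draw CSF for it from consenting children

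*Combined protocol and SAP*

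**What the plan says.** Section 7.2.4.1 gives the collection instruction: "Samples of CSF for ctDNA will be collected in standard CSF collection kit via the Ommaya reservoir at screening and at the EOT Visit". The only condition is the patient's consent to DNA analysis. Samples are to be "stored at site until testing at a central facility". The section closes with the version 8 change: "As per protocol version 8, this analysis will not be performed, and samples should no longer be shipped from sites".

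Other places that still carry the sample:

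- Section 7 caps CSF at 20 mL per dosed patient over the trial, then adds: "In case the patient will participate in the ctDNA analysis, additional 3-5 ml CSF will be collected".
- Section 7.2.4 says: "Samples of CSF for cytology, total protein, glucose, ctDNA, and cell count should be collected according to the Schedule of Assessments".
- The Synopsis, under dosimetry, imaging and laboratory evaluations, lists "CSF sampling for cytology, total protein, glucose, circulating tumor DNA (ctDNA; if the patient has given informed consent to this analysis), and cell count". Sections 3.1.1 (Part 1) and 3.1.3 (Part 2) list the ctDNA sample with the same consent condition.
- Appendix 2, under Informed Consent, still provides for a separate consent form covering ctDNA and primary tumor DNA. The primary tumor DNA analysis is also cancelled, in section 7.2.7.2.

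Appendix 3 differs. The CSF row in each of Tables 6, 7 and 8 names cytology, then "total protein, glucose, and cell count", with no ctDNA. The abbreviation lists under those tables still define ctDNA.

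**The concern.** The version 8 sentence stops what happens to the sample after it is drawn and leaves the draw itself in place. The same sentence is used in sections 7.2.7.1 and 7.2.7.2 for archival tumor tissue. It is adequate there, because that tissue was already obtained as standard of care and stopping shipment ends the trial procedure. The ctDNA sample is taken from the child for the trial, so the step that burdens the patient survives the cancellation.

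Families could be asked to consent to, and children aged 3 to 19 could give, additional CSF with no scientific return. Because the schedule points the other way, sites may also act differently from one another. Samples already held on site have no stated end to their storage, since the central testing they await will not take place.

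The protocol itself treats CSF volume as something to limit. It sets a trial maximum, it moves baseline samples off the dosimetry day to avoid large withdrawals (Table 6, footnotes 13 and 17), and it asks for conservative immunogenicity sampling because of the patients' age (section 7.2.8).

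**Working it through.** There is no sample size, power or error rate to reproduce. The check sets the current texts side by side and then sizes the extra volume.

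**Step 1. What each place tells a site to do**

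| Place | ctDNA CSF sample |
|---|---|
| Synopsis; sections 3.1.1 and 3.1.3 | Listed, if consented |
| Section 7 | Additional 3 to 5 mL for participants in the analysis |
| Section 7.2.4 | To be collected, timing deferred to Appendix 3 |
| Section 7.2.4.1, first part | To be collected at screening and EOT, if consented; stored at site |
| Section 7.2.4.1, version 8 sentence | Analysis and shipment cancelled; collection not mentioned |
| Appendix 2, Informed Consent | Separate DNA consent form still issued |
| Appendix 3, Tables 6 to 8, CSF rows | Not listed |
| Appendix 1, CSF analytes | Not listed |

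**Step 2. Do these reconcile?** Section 7.2.4 sends the site to a schedule that has no ctDNA entry. Section 7.2.4.1 names its own visits and does not depend on the schedule. A site working from the schedule draws nothing; a site working from section 7.2.4.1 draws the sample. No sentence says which prevails, and none says that collection stops. The document is version 8.0, so this is current text and not a record of superseded wording.

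**Step 3. Can the condition for collection still be met?** Yes, in two ways. A child who signed the DNA consent under an earlier version already satisfies it at the EOT Visit. A child newly screened under version 8 can satisfy it because Appendix 2 still provides for the form.

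**Step 4. Size of the extra volume**

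Inputs: 3 to 5 mL additional CSF and the 20 mL maximum (section 7); two visits (section 7.2.4.1); "approximately 0.5 mL of CSF and 2 mL of peripheral blood drawn at each timepoint mentioned in" Table 4 (section 7.2.2).

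- Against the maximum, if 3 to 5 mL is the total: 3/20 = 15% and 5/20 = 25%.
- Against the maximum, if it is per draw: 2 × 3 = 6 mL and 2 × 5 = 10 mL, so 6/20 = 30% and 10/20 = 50%.
- In dosimetry-size samples, taking 3 to 5 mL as the total: 3/0.5 = 6 and 5/0.5 = 10.
- Table 4 CSF timepoints: baseline, 30 min, 1 h, 4 h, 24 h, 48 h, 72 h, Day 5-7 and Day 15, which is 9. The series takes 9 × 0.5 = 4.5 mL. The ctDNA volume as a total is 3/4.5 = 67% to 5/4.5 = 111% of it.

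The text does not say whether the volume is a total or per draw, so both readings are shown.

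**The case against.** The strongest reply is that the collection text has lost its object. Every mention is tied to consent to, or participation in, the DNA analysis, and section 7.2.4.1 says in the same short section that the analysis will not be performed. On that reading no newly screened child can take part, so the extra volume in section 7 is never triggered. The three schedule tables and the Appendix 1 CSF list all omit ctDNA, section 7.2.4 defers to the schedule, and section 7 makes adherence to the schedule a requirement. What remains would then be leftover narrative. This is a fair reading of what the sponsor probably meant. It does not remove the defect: omission from a table is not a cancellation, section 7.2.4.1 is the specific section with its own timepoints, and the consent form is still to be issued.

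A second reply concerns burden. CSF is already taken at screening and EOT for cytology, protein, glucose and cell count, so the ctDNA aliquot adds volume but no visit and no new access route. That stands. The comparison with 0.5 mL dosimetry samples also makes the volume look large; the share of the 20 mL maximum is the more neutral measure.

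Third, the consent forms, laboratory instructions and any version 8 communication to sites are not among these documents and may already deal with this. That also stands, so how many children would be affected is unknown. For stored samples, section 4.3.2.1 lets patients request destruction of untested material, but it gives sites no default instruction.

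Finally, the older text may have been kept to describe samples taken under earlier versions. If so, one explicit sentence ending collection would meet the main point, and the history can be retained if it is marked as past.

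**Conclusion.** The concern holds. Version 8.0 withdraws the ctDNA analysis and the shipment and leaves the instruction to collect. The schedule's silence conflicts with that instruction and does not settle it. Followed as written, section 7.2.4.1 takes an additional 3 to 5 mL of CSF from a consenting child (or 6 to 10 mL, if the figure is per draw and both draws are made) for no result.

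The consequence is one of patient burden, consent and consistency between sites. No endpoint, analysis set or estimate changes. The point should be corrected but does not bear on the validity of the trial. That the text lacks a stop instruction is certain. That any site would act on the remaining wording is an assumption these documents cannot test.

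**What to change.** 1. In section 7.2.4.1, state that CSF for ctDNA is no longer collected from version 8 onward, including at the EOT Visit for patients who consented earlier.
2. Remove ctDNA sampling from the Synopsis and sections 3.1.1, 3.1.3 and 7.2.4 (heading and text), and delete the additional 3 to 5 mL allowance in section 7. If a record of earlier practice is wanted, keep it in the past tense.
3. In Appendix 2, withdraw the separate consent form for ctDNA and primary tumor DNA, since both analyses are cancelled. Drop ctDNA from the abbreviation lists under Tables 6 to 8.
4. Say what sites should do with ctDNA CSF already in storage.

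The cost is a set of text edits in the next amendment and a short letter to sites, which can go out first. No scientific information is given up, because the analysis has already been cancelled.
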